
Criteria for Evaluation: (Efficacy, safety, stopping rules, etc.)
	
Subjects will be screened at week -4, then evaluated for end points at weeks 0, 6 and 12. Follow up phone call will be done 30 days after last dose of study drug to assess for adverse effects.
 
Study participation will be stopped for adverse effects at the discretion of the study investigator. Subjects may stop study participation at any time and for any reason.

Statistics:
	
The total sample size is requested, after accounting for attrition over the 12-week period, is 20 subjects per group or 40 subjects total. Sample size estimates were based on the effects of exercise on CD34+/KDR+ cells as described in the literature. The effect of a single session, as well as extended training, on healthy subjects or those with existing cardiovascular conditions appears to increase the CD34+/KDR+ cells.
 
This is a pilot study as a result appropriate power calculation is not feasible. We however did conduct power analysis, which provided us with 73% power (see statistics section). A p-value of less than 0.05 will be considered statistically significant.

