5 STATISTICAL CONSIDERATIONS

Statistical Analysis:

Sample Size Estimation:

The total sample size requested, accounting for attrition over the 12-week period, is 20 subjects per group or 40 subjects total. We plan to allow for 25% attrition (drop out), therefore plan to screen 55 patients over three years.

Sample size estimates were based on the effects of exercise on CD34+/KDR+ cells and VEGF, as described in the literature (47-50).

This is a pilot study and accurate power calculation is not feasible.

The effect of a single session, as well as extended training, on healthy subjects or those with existing cardiovascular conditions appears to increase the CD34+/KDR+ cells and VEGF.

To compute sample size we used the approach suggested by Diggle, Liang, & Zeger (1994)(51) which compares the rates of change in the two study groups over time. This approach incorporates the number and interval of time points and the correlation among repeated measures. For this study, we will employ one baseline and two follow-up measures at 6 and 12 weeks. Further, we will assume a correlation 0.60 among repeated measures of the outcome. We consider this a conservative estimate since Frison and Pocock (1992) (52) suggest a correlation of 0.65 as reasonable in the absence of an existing estimate. We also note that as this correlation increases, statistical power also increases.

The results in the table below show the expected mean difference in study groups at the end of follow-up, as well as the average rate of change in the two groups at 80% power and 90% power. To estimate the effect of Linagliptin on the CD34+/KDR+ cells, we expect that the effect would be at least 25% greater than the effect seen for exercise alone. Using the results from Sandri et al. (2005)⁴⁹ for the rate of change and the variability, the CD34+/KDR+ cells increased an average rate of about 4/wk with a standard deviation of about 15. Thus, for a 25% increase in the rate of change for the CD34+/KDR+ cells due to Linagliptin, a sample size of 18 subjects per group would provide about 84% power, assuming measures taken at baseline and 2 equally-spaced time points over 12 weeks. At the conclusion of follow-up, we would expect study groups to differ by an average of 12 cells. If the effect of Linagliptin is only 20%, a sample of 18 would provide about 70% power, whereas a sample of 20 would provide about 73% power.

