To estimate the effect of linagliptin on CD34+/KDR+ cells, we originally proposed a sample size of 20 per group in 2 groups, giving us power = .73, assuming alpha=.05, between time points of .60 and equal allocation between groups. Thus, the group x time interaction effect size we were modeling was an interaction that explained 3% of total variance, or a partial eta-square = .0291. Using 3 groups (Insulin only, metformin only, metformin + insulin), with the same effect size, we would achieve this same level of power using a total sample size of 51 (17 per group). However, given the relatively small numbers of potential participants with insulin-only (n=21) and insulin+metformin (n=54), and the relative large number with Metformin only (260), we will need to change the allocation ratio between groups. Maintaining the same total sample size as originally proposed (40), we will allocate patients from each group in the following numbers: **Metformin only (22), Metformin+insulin (12), Insulin only (6)**. We recognize that we will be underpowered for comparisons between the Metformin + insulin versus Insulin groups. However, comparisons with the Metformin-only group will still have reasonable power. Given the small number of potential patients with Insulin-only, this is a feasible strategy for including this group in the analysis.

Data Analysis.

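### The same 73% power is attached to two different effect sizes, and the claim of reasonable power does not hold for Metformin-only versus Insulin-only (22 v 6)

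*Combined protocol and SAP*

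**What the plan says.** **Synopsis, Statistics.** After noting that this is a pilot, it reports: "We however did conduct power analysis, which provided us with 73% power (see statistics section"). It adds: "A p-value of less than 0.05 will be considered statistically significant".

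**Section 5, Sample Size Estimation.** The cited longitudinal method is one "which compares the rates of change in the two study groups over time". Measurements are at weeks 0, 6 and 12, with correlation 0.60, a reference slope of 4 cells/week and an SD of about 15. For a linagliptin effect of only 20%, 18 per group is said to give about 70% power, "whereas a sample of 20 would provide about 73% power".

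**Section 5, Sub-Group Subject Number Breakdown.** It restates the two-group design as "giving us power = .73, assuming alpha=.05". From this it infers that the effect being modelled was "an interaction that explained 3% of total variance, or a partial eta-square = .0291". For three background-therapy groups it says that "with the same effect size, we would achieve this same level of power using a total sample size of 51 (17 per group"). The total is then held at 40, split into 22 Metformin only, 12 Metformin + insulin and 6 Insulin only. Low power is admitted for 12 v 6, and the next sentence is: "However, comparisons with the Metformin-only group will still have reasonable power". No power is given for 22 v 6 or 22 v 12.

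**The concern.** The sub-group paragraph presents .0291 as another way of writing the effect behind the 73%. If it is a different effect, the same power is being quoted for two quantities, and the three-group total says nothing about the 20% effect. A reader of the synopsis would also take 73% to belong to the usual two-sided test at 0.05.

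The second problem lies in the group sizes. The smaller group dominates the precision of an unequal comparison. Moving from 12 v 6 to 22 v 6 leaves the group of 6 in place, so it is hard to see how one can be underpowered and the other reasonable. A null result for Metformin-only versus Insulin-only could then be read as evidence of no difference.

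**Working it through.** **Inputs (Section 5).** SD 15; correlation 0.60; times 0, 6, 12, so the sum of squares about the mean time is 36 + 0 + 36 = 72; slope 4/week, so 20% is 0.8 and 25% is 1.0 cells/week; alpha 0.05; groups of 22, 12 and 6.

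**1. Reproducing the 73%.** The variance of one patient's slope is 15² × (1 − 0.60)/72 = 90/72 = 1.25. For 20 per group, SE = √(1.25 × 2/20) = 0.354, and z = 0.8/0.354 = 2.26.
- One-sided 5%: Φ(2.26 − 1.645) = 0.732
- Two-sided 5%: Φ(2.26 − 1.960) = 0.619

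The other stated powers show the same pattern (VEGF uses SD 5 and 0.3 pg/mL per week):

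| Case | Stated | One-sided | Two-sided |
|---|---|---|---|
| 0.8 cells/week, 18 per group | 0.70 | 0.692 | 0.574 |
| 1.0 cells/week, 18 per group | 0.84 | 0.850 | 0.765 |
| 1.0 cells/week, 22 per group | 0.90 | 0.907 | 0.843 |
| VEGF, 18 per group | 0.77 | 0.779 | 0.675 |
| VEGF, 27 per group | 0.90 | 0.905 | 0.841 |

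These powers therefore fit a one-sided slope test.

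**2. Converting .0291 to a slope.** The paragraph speaks of total variance. With two equal groups and a linear difference d, f² = (d/2)² × (72/3)/15² = 6d²/225, and eta² = f²/(1 + f²).
- d = 0.8: f² = 0.0171, eta² = .0168
- d = 1.0: f² = 0.0267, eta² = .0260
- eta² = .0291: f² = 0.0300, d = √(0.0300 × 225/6) = 1.06 cells/week (26.5% of 4/week)

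**3. Reproducing .73 and 51.** Use a group × time F test with λ = f² × M × 3/(1 − 0.60) and df 2(k − 1) and 2(N − k). M is N − k or N, depending on convention.

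| Effect | Design | λ (M = N − k) | Power | Power (M = N) |
|---|---|---|---|---|
| .0291 | N = 40, two groups | 8.54 | 0.729 | 0.753 |
| .0291 | N = 51, three groups | 10.79 | 0.729 | 0.758 |
| 0.8 cells/week | N = 40, two groups | 4.86 | 0.476 | 0.497 |

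So .73 and 51 agree with each other through .0291. The same test at 0.8 cells/week gives about 48% to 50%. Conversely, the slope test of step 1 at 1.06 cells/week with 20 per group gives 0.91 one-sided.

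**4. Comparisons between background-therapy groups.** SE = √(1.25 × (1/n₁ + 1/n₂)); equivalent n per group = 2/(1/n₁ + 1/n₂). Powers are unadjusted.

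| Pair | SE | Equivalent n | 0.8, two-sided | 0.8, one-sided | 1.06, two-sided | 1.06, one-sided |
|---|---|---|---|---|---|---|
| 22 v 6 | 0.515 | 9.4 | 34% | 46% | 54% | 66% |
| 12 v 6 | 0.559 | 8.0 | 30% | 42% | 47% | 60% |
| 22 v 12 | 0.401 | 15.5 | 51% | 64% | 75% | 84% |

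The SE ratio of 22 v 6 to 12 v 6 is √(0.2121/0.2500) = 0.92. It depends only on the group sizes, not on SD, correlation or effect. The Data Analysis section adjusts pairwise tests for multiplicity without naming a method. If Bonferroni over three pairs is assumed, 22 v 6 falls to 20% at 0.8 and 37% at 1.06.

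**5. Two-sided power for the randomised comparison at 0.8 cells/week.** 20 per group: 62%. The planned 18 completers: 57%. With the 25% attrition also mentioned, 15 per group: z = 0.8/√(1.25 × 2/15) = 1.96, so 50%.

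**The case against.** **The 73% is not baseless.** A reader might infer that it is simply wrong for the 20% effect. The documents do not support that: one effect and one method are named, and the figure reproduces to two decimals one-sided. What is missing is the label. A two-sided route also comes close: forcing a shared baseline gives 0.723. However, the model in Data Analysis carries a separate Group term.

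**48% is not the true power.** That figure applies an F test which Sample Size Estimation never uses for 0.8 cells/week. It shows only that the two 73% statements are not interchangeable.

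**1.06 cells/week is derived, not stated.** It needs SD 15, a linear difference and the total-variance reading. That reading is the paragraph's own wording. The within-patient reading gives only about 24% at N = 40 (λ = 0.0300 × 76 = 2.28), so it does not reproduce .73. It also puts .0291 at 0.55 to 0.67 cells/week depending on convention, again not 0.8. The mismatch survives either way.

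**Not every Metformin-only comparison is weak.** For 22 v 12, reasonable is a fair word at 1.06 cells/week, though not at 0.8. For 22 v 6, a large enough difference would be detectable (80% two-sided needs about 1.44 cells/week), but the plan states no such difference.

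**The study is a declared pilot.** The plan says accurate power calculation is not feasible and calls the 22/12/6 split a feasibility strategy. This stands, and it limits the consequence. It does not justify quoting one power for two effects.

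**Conclusion.** The point holds and is minor.

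- The 73% for the 20% effect is correct one-sided and about 62% two-sided at 20 per group, and no sidedness is given.
- The .0291 in the sub-group paragraph is not that effect. On the paragraph's own total-variance wording it is about 1.06 rather than 0.8 cells/week. The total of 51 is consistent with .0291 but does not carry over to the 20% effect. A change of test is the likely cause; the documents do not say so.
- Reasonable power is unsupported for Metformin-only versus Insulin-only, whose power is only about 4 to 7 percentage points above that of the comparison the plan calls underpowered. For Metformin-only versus Metformin + insulin it depends on a slope difference that is not stated.

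The effect-size result assumes SD 15, correlation 0.60 and a linear difference. The 0.92 ratio rests on group sizes alone. A reader might go on to infer that 40 patients is the wrong number or that the linagliptin-placebo comparison is compromised; neither follows.

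**What to change.** Wording only:

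1. In the synopsis, Sample Size Estimation and the sub-group paragraph, name one effect, one test and its sidedness. Either label 73% as one-sided, or give the two-sided power for 0.8 cells/week: about 62% with 20 per group before attrition, 57% with 18 completers, 50% with 15 (25% attrition).
2. In the sub-group paragraph, state that .0291 is a larger effect than the 20% effect of Sample Size Estimation, and that the total of 51 applies only to .0291.
3. Replace the two sentences on underpowered and reasonable comparisons with: *Comparisons of Insulin only with either other group will be underpowered; power for Metformin only versus Metformin + insulin depends on the slope difference.*

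The cost is a less favourable stated power if a two-sided test is named. Sample size, allocation and analysis stay as they are. Deleting the 51-patient sentence, or changing the pairwise tests in Data Analysis, is optional and not needed for this correction.

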4.4 Blinding/ Unblinding

Blinding is critical to the integrity of this clinical study. However, in the event of a medical emergency or pregnancy in a subject, **in which knowledge of the investigational product is critical to the subject's management**, the blind **for that subject** may be broken.

Before breaking the blind of an individual subject's treatment, the investigator should have determined that the information is necessary, i.e., that it will alter the subject's immediate management. In many cases, particularly when the emergency is not investigational product-related, the problem may be properly managed by assuming that the subject is receiving active product without the need for un-blinding.

End of Study Unblinding Protocol

Upon completion of the research study, we will undergo the following protocol in order to unblind the research data.

Unblinding is the process by which the allocation code is broken so that the investigator, clinical staff and the trial statistician becomes aware of which intervention each subject enrolled in the research study was taking.

Unblinding at the end of the study is required in order to make unmasked analysis in accordance with the study analysis plan. It is also conducted in order to inform the participants of which investigational product they were assigned to.

Time to unblind:

Unblinding shall be conducted when all subjects enrolled in the research study have finished treatment, and all follow up visits. There must be no plan to recruit any more subjects in the research study. Additionally, all data points and outcome measures for each research subject must have been collected, and ideally compiled. Prior to unblinding there will be a data lock on clinical outcome measures and basic side outcome measures and associated research data collected for the study.

Procedure to unblind

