The distributional assumptions of all measures will be examined. Means and standard deviations will be computed for continuous measures and proportions for categorical variables. Graphical representations of the mean group slopes and individual slopes will be generated and inspected. Study groups will be compared to determine whether any imbalance between the groups on patient characteristics remain after randomization. If imbalance is evident, by inspection, all models will be adjusted for the unbalanced covariates. Change in outcome over time will be examined using a multilevel approach with linear mixed models (LMM) (53, 54). The longitudinal multilevel modeling approach will enable us to examine characteristics of within-person change, as well as between-group differences that may influence change. LMMs handle missing data more efficiently than traditional ANOVA designs. In the linear mixed models, the patient is considered a random effect and the outcome measured at specific time points is nested within patient. In an initial model containing only the variable TIME, we will use a likelihood ratio test to determine whether a random effect for time should be modeled.

The model below represents a random intercept for patient and a random coefficient for TIME.

$$Y_{ij} = \beta_0 + \beta_1 Time_{ij} + u_{i0} + u_{i1} Time_{ij} + \varepsilon_{ij}$$

We will examine whether TIME may be modeled linearly by testing the added contribution of TIME (represented with two indicator variables) to a model with TIME as a single continuous variable. Assuming time may be modeled as a continuous variable, subsequent analyses will add study group and other patient characteristics as covariates. We are particularly interested in whether there is a significant interaction between study group and time, adjusting for other patient level covariates. A significant interaction would indicate that the slopes in outcome over time differ by study group. If the global test of interaction is significant, subsequent significance testing of the pairwise comparisons of group slopes group will be adjusted for multiple comparisons. The model also includes coefficients for the group-by-time interactions and random effects for patient and time.

$$Y_{ij} = \beta_0 + \beta_1 Time_{ij} + \beta_2 Group_i + \beta_3 (Time_{ij} \times Group_i) + u_{i0} + u_{i1} Time_{ij} + \varepsilon_{ij}$$

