In the event that TIME is modeled using indicator variables, two indicator variables will be used to represent the three time points, with baseline serving as the reference category. The interaction between GROUP and TIME will be modeled in a similar fashion using two additional indicator variables. The above multivariable model enables us to adjust for time-varying covariates, such as glucose. Since glucose will be measured contemporaneously with the outcomes at each visit, however, causal interpretations of glucose and any outcome are suspect. As such, we will consider glucose as a nuisance covariate, and consider any relationship between glucose and an outcome as merely associative.

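### The covariate rule for baseline imbalance, on its natural reading, does not act on the Time x Group test, and it leaves the choice of covariates to the eye

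*Combined protocol and SAP*

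**What the plan says.** All of this is in Section 5, Data Analysis, unless another section is named.

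- **Treatment test.** "We are particularly interested in whether there is a significant interaction between study group and time, adjusting for other patient level covariates". The reading of that coefficient is given too: "A significant interaction would indicate that the slopes in outcome over time differ by study group".
- **Imbalance rule.** "If imbalance is evident, by inspection, all models will be adjusted for the unbalanced covariates". The rule gives no list of covariates, no threshold and no form of adjustment.
- **How covariates enter.** Once time is accepted as continuous, "subsequent analyses will add study group and other patient characteristics as covariates".
- **Model terms.** "The model also includes coefficients for the group-by-time interactions and random effects for patient and time". Neither displayed equation contains a covariate, and no covariate-by-time term is mentioned. If time is categorical, two indicators and their products with group replace the linear terms.
- **Time-varying covariates.** "The above multivariable model enables us to adjust for time-varying covariates, such as glucose".
- **Visits** (Sample Size Estimation). "we will employ one baseline and two follow-up measures at 6 and 12 weeks".
- **Allocation.** Section 4.2 describes permuted blocks and names no stratification factor. The sub-group breakdown in Section 5 plans 22 patients on metformin only, 12 on both drugs and 6 on insulin only.

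**The concern.** A main effect moves a patient's whole profile up or down. The treatment test compares rates of change. A patient-level covariate added without its time interaction therefore cannot take an imbalance in slope-related factors out of the tested coefficient. A report could state that the result was adjusted for imbalance although the coefficient never moved.

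The second issue is selection. Data Analysis describes inspecting plots of group and individual slopes just before it describes the imbalance check, and Section 4.4 says: "Unblinding at the end of the study is required in order to make unmasked analysis in accordance with the study analysis plan". Nothing fixes the covariate set beforehand, so two analysts could adjust for different factors.

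**Working it through.** **Inputs from Section 5.** SD 15; correlation 0.60; weeks 0, 6, 12; planned slopes 4 v 5 cells/week (difference 1/week, 12 cells at week 12); 20 enrolled and 18 completing per arm; 18 insulin users of 40 (12 + 6).

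**The plan's own figure first.** The squared time deviations sum to 36 + 0 + 36 = 72. The per-patient slope SD is 15 × √(0.40/72) = 1.118. With 18 per arm, SE = 1.118 × √(2/18) = 0.373, and 1/0.373 = 2.683.

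- One-sided 0.05: Φ(2.683 − 1.645) = 0.850, against 0.84 stated.
- Two-sided 0.05: Φ(2.683 − 1.960) = 0.765.

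The stated power is reproduced only with a one-sided test. That is a separate matter; the inputs are the right ones for what follows.

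**Why the main effect drops out.** With three equally spaced complete visits, a patient's fitted slope is (Y₁₂ − Y₀)/12. A term γXᵢ adds the same amount to Y₀ and Y₁₂ and cancels. Time x Group is the difference between arms in mean slope, so it does not depend on γ. With indicator time, the same cancellation holds for each change from baseline.

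**Numerical check, complete data.** Over 1,500 simulated trials per setting, adding the main effect changed Time x Group by less than 1e-15, under compound symmetry and under a random intercept plus slope. In four data sets fitted by REML the coefficient agreed to five decimals. The SE is identical for given variance components. When these were re-estimated it was unchanged with a random intercept only, and moved slightly in three of the four random-slope fits (for example 0.4107 to 0.4189).

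**Illustration with background therapy (assumed slope effect).** Let insulin users' slope be higher by 1 cell/week, with 12 users in the placebo arm and 6 in the linagliptin arm.

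- Shift in Time x Group: 1 × (12/20 − 6/20) = 0.3 cells/week; × 12 weeks = 3.6 cells; 3.6/12 = 30% of the planned difference.
- SE without the covariate-by-time term: 1.118 × √(2/20) = 0.354.
- Variance inflation with it: total sum of squares of the covariate 40 × 0.45 × 0.55 = 9.9; within arms 20 × 0.6 × 0.4 + 20 × 0.3 × 0.7 = 9.0; ratio 1.10. SE = 0.354 × √1.10 = 0.371, about 5% larger.

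| Model | Expected Time x Group (true 1.00) | SE |
|---|---|---|
| No covariate | 0.70 | 0.354 |
| Main effect | 0.70 | 0.354 |
| Main effect and covariate x time | 1.00 | 0.371 |

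**Dropout.** For a continuous covariate, assume a 0.5 SD imbalance and an effect of 0.5/week per SD on slope. Estimates are means over simulated trials, compound symmetry, true value 1.00.

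| Dropout | No covariate | Main effect | Covariate x time | Mean absolute change from main effect |
|---|---|---|---|---|
| 0% | 1.255 | 1.255 | 1.006 | 0 |
| 10% | 1.264 | 1.264 | 1.012 | 0.019 |
| 25% | 1.251 | 1.251 | 1.000 | 0.034 |

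With a random slope the mean absolute changes are 0.027 and 0.045 per week; the largest single change was 0.27. Single estimates move under dropout, but the average shift stays.

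**Level-only factor.** If the covariate affects level but not slope, complete data give 1.009 in all three models. There is nothing to correct.

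**Chance of imbalance.** Insulin users split 12:6 or worse: hypergeometric (40, 18, 20), 0.111. One continuous covariate differing by at least 0.5 SD: 2 × [1 − Φ(0.5/√0.1)] = 0.114. At least one of five independent covariates: 1 − 0.886⁵ = 0.45; of ten, 0.70. These count any imbalance, whether or not the factor affects slope.

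**The case against.** - **A reader might infer that the plan is unable to correct imbalance.** The documents do not support that. Nothing limits the covariates to main effects, the equations show no covariate at all, and the text states an interest in between-group influences on change. The sub-group breakdown even discusses a group-by-time effect across the three therapy groups, so a therapy-by-time term may have been in mind; whether it would sit in the treatment model is not said. This stands: the defect is an unspecified form of adjustment whose natural reading is inert.
- **A reader might infer that any chance imbalance biases the result.** It does not. Level-only imbalance is removed by the within-patient contrast, and randomization protects the test over repeated trials. Simulating the insulin scenario with no treatment effect and an unadjusted two-sided t-test on patient slopes gave about 4.9% type I error overall, rising to about 11% only within the 11% or so of trials split 12:6 or worse. This stands as well.
- **The size is assumed.** A slope effect of 1 cell/week equals the whole planned treatment difference, and the documents name no factor that predicts slope. The 30% is an illustration. Sex may also be better balanced than chance, since Section 3.1 plans as many men as women in both arms.
- **A reader might infer that covariates will be picked after unblinded results are seen.** Section 4.4 requires data lock before unblinding, and Section 5 places the baseline comparison ahead of outcome modelling. The text permits late selection; it does not describe it.
- **Glucose does move the coefficient** (1.864 to 1.440 in one simulated fit). It varies over time and is a separate case from baseline imbalance.

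**Conclusion.** The point holds in a limited form. The rule promises a correction that, with covariates as main effects, leaves Time x Group exactly unchanged for within-patient-constant covariates at complete visits. At 10-25% dropout it does not on average remove a slope-related imbalance. It also leaves covariate choice to visual judgement.

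The unadjusted randomized comparison remains valid, so what is at risk is the accuracy of this trial's estimate given its own imbalance, and the credibility of any claim of adjustment. The illustrative size, 0.3 cells/week or 3.6 cells at week 12, rests on an assumed 1 cell/week slope difference for insulin users and a split that has about an 11% chance. For a self-described pilot of 40 patients this is a should-fix.

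**What to change.** Replace the inspection rule in Section 5 with text that does the following:

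1. Names a short covariate set, fixed before unblinding, from data already collected: for example background-therapy group and sex.
2. Enters each covariate with its covariate x time term; if time is categorical, with both time indicators.
3. Reports the model without covariates alongside the adjusted one, and states in advance which of the two is primary.
4. Keeps baseline tables descriptive, with no bearing on model choice.
5. Treats glucose separately, as a time-varying covariate outside the imbalance rule.

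**Cost.** Wording only; no new data. With linear time, three-level therapy and sex add 3 main-effect and 3 time-interaction coefficients (2 + 1 of each). With indicator time the interactions double to 6. The SE rises by about 5% for a single two-level covariate split 12 v 6, and by less when it is better balanced. With only 6 insulin-only patients, the two insulin groups could be combined into one indicator if the three-level term is too thin; that choice should also be fixed in advance.

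### The planned slope comparison leaves baseline unadjusted, giving up about 8-9 points of two-sided power at the plan's own inputs; separately, the plan is unclear whether the random slope is tested or always kept

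*Combined protocol and SAP*

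**What the plan says.** Section 5, Data Analysis, sets out a sequence.

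- In a model with time only, "we will use a likelihood ratio test to determine whether a random effect for time should be modeled".
- Next comes the shape of time: "We will examine whether TIME may be modeled linearly by testing the added contribution of TIME" as two indicators to a model with time as one continuous term.
- Study group is then added. The treatment question is the group-by-time interaction. The final equation has an intercept, Time, Group, Time × Group, a random intercept and a random slope. The text beside it also lists random effects for patient and time, without making the slope depend on the likelihood ratio result.
- The alternative branch: "In the event that TIME is modeled using indicator variables, two indicator variables will be used to represent the three time points", with two further indicators for the interaction.

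Baseline is one of the three repeated outcomes. It is not a covariate, and the arms' baseline means are not constrained to be equal. No degrees-of-freedom method is given.

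For the sample size, Section 5 states that "the CD34+/KDR+ cells increased an average rate of about 4/wk with a standard deviation of about 15", assumes a correlation of 0.60, and powers for 4 against 5 cells per week, or 12 cells at week 12. It reports that "a sample size of 18 subjects per group would provide about 84% power". The Synopsis (Statistics) says "A p-value of less than 0.05 will be considered statistically significant", and the sub-group paragraph of Section 5 has "giving us power = .73, assuming alpha=.05". Neither says whether the test is one-sided or two-sided.

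**The concern.** There are two separate issues, with different causes.

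The first is efficiency. Randomisation makes the expected baseline means equal. A free Group term estimates a baseline difference whose true value is zero, and so discards information. In a trial of 40 patients recruited over about three years, that precision would cost nothing to recover, because the baseline is already measured.

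The second is pre-specification. The text both tests for the random slope and writes it in regardless. If the test governs, a real but moderate random slope will often go undetected at this size, and the standard error of the slope difference is then too small. The linearity test also leaves open whether the main treatment test has 1 or 2 degrees of freedom.

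**Working it through.** **Inputs.** From Section 5: SD 15, correlation 0.60, slope difference 1 cell/week (12 cells at week 12), visits at weeks 0, 6 and 12, 18 or 20 per arm. The sum of squared time deviations is 36 + 0 + 36 = 72. A random-slope variance is not given; wherever one appears below it is an assumption.

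**Reproducing the plan's power.** SE of the slope difference = √[2·SD²(1−ρ)/(72n)]. At n = 18: √[2·225·0.4/1296] = 0.3727, and 1/0.3727 = 2.683.

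- One-sided 0.05: Φ(2.683 − 1.645) = 85%, against the stated 84%.
- For the 20% effect the plan says "a sample of 18 would provide about 70% power, whereas a sample of 20 would provide about 73% power"; the same one-sided formula gives 69% and 73%.
- Two-sided 0.05: Φ(2.683 − 1.960) = 76.5% at n = 18, and 57% and 62% for the 20% effect.

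The stated powers therefore match a one-sided 5% test. The comparison below is two-sided unless noted.

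**Why the slope contrast is a change score.** With complete data each patient's least-squares slope is (−6·y₀ + 0·y₆ + 6·y₁₂)/72 = (y₁₂ − y₀)/12. With a free Group term, the interaction is the arm difference in this quantity.

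**Variance per patient of the week-12 comparison.**

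- Change score: 2(1 − 0.6)·225 = 180.
- Baseline-adjusted: (1 − 0.36)·225 = 144, which is 20% smaller. Since 180/144 = 1.25, 18 per arm with adjustment is worth about 22.5 without it.

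**Power, two-sided noncentral t, 12 cells.**

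| n per arm | SE, change | SE, adjusted | Power, change | Power, adjusted |
|---|---|---|---|---|
| 18 | √(2·180/18) = 4.47 | √(2·144/18) = 4.00 | 74.1% | 82.9% |
| 20 | √(2·180/20) = 4.24 | √(2·144/20) = 3.79 | 78.7% | 86.8% |

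The gain does not require leaving the slope. Keeping linear time and dropping only the Group main effect gives, by normal approximation, 76.5% to 85.7% at 18 per arm and 80.7% to 89.1% at 20.

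**How the gain at 18 per arm moves.**

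- Correlation 0.4: about 15 points; 0.65: 7; 0.7: 5; 0.8: 1.5.
- One-sided 0.05, normal approximation: 85% to 91%, about 6 points.
- Assumed random-slope SD of 0.6 cells/week, independent of baseline and added to the plan's covariance: the variances become 180 + 144·0.36 = 231.8 and 144 + 51.8 = 195.8, and power goes from 63.2% to 70.4%.
- Assumed random-slope SD of 1.0: the variances are 324 and 288, and power goes from 49.3% to 54.0%. Across this range the gain is about 5-7 points.

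**Type I error if the likelihood ratio test governs.** The full sequence was simulated with complete data, 100,000 trials per scenario, at 18 per arm.

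| True slope variance, (cells/week)² | t reference | z reference |
|---|---|---|
| 0 (the plan's exchangeable 0.60) | 4.9% | 5.4% |
| 0.3-1.25 (assumed) | 5.7-5.9% | 6.1-6.5% |
| 2.5 (assumed) | 5.1% | 5.8% |

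A separate simulation at 20 per arm, with assumed slope SDs of 0.6-1.0 (variances 0.36-1.0), gave 5.9-6.0% (t) and 6.3-6.6% (z). A random-slope t test fixed in advance stayed at 4.9-5.2%. The 5.4% in the first row reflects the z reference, not model selection. With a curved time trend common to both arms, so that the linearity test often rejects, the sequence stayed at 4.9-5.2% (t).

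**Cost of the 2-df branch.** If the effect is linear, the noncentrality is 2.683² = 7.2 whether the test has 1 or 2 degrees of freedom. On 2 df that gives about 65% (F) to 67% (chi-square) power at 18 per arm, against 74-77% on 1 df.

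**The case against.** A growth model with a free baseline is a standard choice and is unbiased under randomisation. The study calls itself a pilot. The plan regards 0.60 as a conservative correlation, and at 0.8 the gain almost vanishes. The change-score identity is exact only for complete data, and the plan expects attrition. Replacing the slope with a week-12 contrast would alter the quantity the sample size was built on. All of this stands. It limits the size of the point and argues against forcing a week-12 contrast; it does not justify the free Group term.

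A reader might infer more: that two pre-tests inflate type I error and that the plan loses 8-9 points of power besides. The documents do not support this.

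- Inflation needs a random-slope variance that they do not give, and it is absent under the covariance they state.
- The final equation keeps the random slope. If that governs, this source of inflation disappears.
- The linearity test is described before study group enters, and it adds essentially no inflation.
- The power loss comes from the free Group term, not from the pre-tests.
- The two effects do not peak together: where slopes vary enough to produce inflation, the gain from adjustment is about 5-7 points.

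The plan does allow covariates where imbalance is seen on inspection. That is a further data-driven step, and it does not commit to adjusting for the baseline outcome.

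**Conclusion.** The point holds as one of efficiency and pre-specification, not validity. At the plan's SD, correlation and 12-cell difference, and assuming a two-sided 0.05 test, ignoring baseline costs about 9 points of power at 18 per arm (74% against 83%) and 8 at 20 (79% against 87%). The size depends mainly on the correlation, as shown.

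The type I concern is conditional and mild. It requires that the likelihood ratio test override the written equation and that slope variance lie around 0.3-1.25 (cells/week)². Type I error is then about 5.7-6.0% with a t reference, or 6.1-6.6% with z. What the text does establish is an inconsistency about the random slope, an unstated reference distribution, and a main test whose degrees of freedom are left open.

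**What to change.** In Section 5, Data Analysis:

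1. Drop the Group main effect, so that both arms share a baseline mean, or use the baseline outcome as a covariate with weeks 6 and 12 as responses.
2. Delete the likelihood ratio pre-test. Always keep the random slope, or use an unstructured 3 × 3 covariance (six parameters), with a small-sample method such as Kenward-Roger.
3. Name one primary 1-df contrast in advance and state whether the test is one-sided or two-sided. The 12-week slope difference already used for the sample size can stay. A week-12 difference with categorical time is an option; whichever is not primary becomes the sensitivity analysis. The linearity check can remain as a description that does not select the test.

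The cost is SAP wording only: no new patients, visits or data.
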